9.7.4. Handling of Missing Data

There will be no imputation or replacement of missing data. All analyses will be conducted on observed cases. All patients will be included in the descriptive analysis limited with the information recollect. The missing data will be included in the study report. Analysis with case complete will not be conducted.

9.7.5. Statistical Methods

To achieve the objectives described above, the following methods will be used:

9.7.5.1. Descriptive statistics

Frequencies and percentages will be reported for binary and categorical variables, while medians and interquartile ranges (IQRs) will be reported for continuous variables, i.e., HRU. Finally, it will be presented through a tabular display of summary statistics and will be complemented by the generation of graphs, such as histograms, box plots, violin plots, density plots, scatterplots, depending on the nature of the variable.

On the other hand, difference of means (Student or Welch t-test) or medians (Wilcoxon or Kruskal-Wallí's test) between subgroups will be considered (according to the variable distribution – normal or not), considering the sizes of these groups and trends in the behavior of the measures of centrality and dispersion.

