Frequencies and percentages will be reported for binary and categorical variables, while medians and interquartile ranges (IQRs) will be reported for continuous variables, i.e., HRU. Finally, it will be presented through a tabular display of summary statistics and will be complemented by the generation of graphs, such as histograms, box plots, violin plots, density plots, scatterplots, depending on the nature of the variable.

On the other hand, difference of means (Student or Welch t-test) or medians (Wilcoxon or Kruskal-Wallis's test) between subgroups will be considered (according to the variable distribution – normal or not), considering the sizes of these groups and trends in the behavior of the measures of centrality and dispersion.

• **Milestones**

Completion of feasibility assessment	12 May 2023
Registration in the EU PAS register	15 October 2023
Start of data collection	15 November 2023
End of data collection	30 July 2025
Start date of data analysis	16 September 2024
Study progress report 1	30 August 2024
Interim report 1	30 July 2024
Interim report 2	15 January 2025
Final study report	15 January 2026

PFIZER CONFIDENTIAL

CT24-WI-GL02-RF01 6.0 Non-Interventional Study Protocol Template For Primary Data Collection Study 01-Aug-2023
Page 15 of 57

**CLINICAL AND MEDICAL CONTROLLED DOCUMENT (CMCD)
REQUIRED FORM/TEMPLATE**

Identifier	Version	Title	Effective Date
CT24-WI-GL02-RF01	6.0	NON-INTERVENTIONAL STUDY PROTOCOL TEMPLATE FOR PRIMARY DATA COLLECTION STUDY	01-Aug-2023

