8. RESEARCH QUESTION AND OBJECTIVES

Hypothesis

There are not hypotheses to evaluate.

Research Question

What is the impact of tafamidis use in Colombian patients diagnosed with ATTR-CM on quality of life during two years of follow-up?

Primary objective

To describe the impact of tafamidis use in Colombian patients diagnosed with ATTR-CM on quality of life during two years of follow-up

Secondary objectives

- To describe the clinical and demographic characteristics of the patients at the moment of prescription of tafamidis
- To determine the treatment patterns to manage ATTR-CM before tafamidis prescription
- To evaluate the frequency of hospitalization and its causes during the follow-up period
- To describe the use of cardiovascular devices during follow-up of patients recruited in the study
- To outline the change in baseline for patients in cardiovascular functionality in patients prescribed tafamidis
- To measure the adherence of the patients to the therapy
- To describe the access barriers during the use of tafamidis

Exploratory objectives

- To analyze the relationship between baseline variables and patient and changes of quality of life and cardiovascular functionality

PFIZER CONFIDENTIAL

CT24-WI-GL02-RF01 6.0 Non-Interventional Study Protocol Template For Primary Data Collection Study 01-Aug-2023
Page 20 of 57

CLINICAL AND MEDICAL CONTROLLED DOCUMENT (CMCD) REQUIRED FORM/TEMPLATE

Identifier	Version	Title	Effective Date
CT24-WI-GL02-RF01	6.0	NON-INTERVENTIONAL STUDY PROTOCOL TEMPLATE FOR PRIMARY DATA COLLECTION STUDY	01-Aug-2023

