9. RESEARCH METHODS

9.1. Study design

The study will be a non-interventional, descriptive, and longitudinal prospective study with primary data collection that involves sites/investigators. The patients must be diagnosed before enrollment with ATTR-CM and prescribed with tafamidis following indications approved by National Institute for Drug and Food Vigilance (INVIMA) in Colombia. The patients will be followed up from the index date until patient i) have deceased, ii) have decided to withdraw from the study, iii) have terminated of treatment, iv) have been lost to follow up, or, v) finalize the 24 months of following up, the event that happens first. The index date will be defined as the date for the first prescription of tafamidis.

The patients that were prescribed with tafamidis before August of 2023 will be recruited. In the cases where the patients were prescribed before starting the study, all previous information will be collected from the data provided by the patients. The quality of life will be evaluated when the patient accepts to participate and signs the informed consent.

Quality of life, adherence, concomitant treatment, hospitalization for any causes, cardiovascular functionality will be measured 24 months after the prescription of tafamidis. Twelve months before the index date, treatments, and frequency of hospitalization for any causes will be measured (Table 1).

There will be two sources of information. Clinical and demographic information and death at the baseline will be abstracted from the medical record while the data related to hospitalizations, cardiovascular functionality, quality of life will be collected directly from the patients using validated questionnaires and structured interviews. Thus, in this case the report form (CRF) will serve as a source document.

In patients who have been prescribed with tafamidis more than 1 month and have not received the drug by the HMO yet, the first time of administration of tafamidis will be considered in the analysis. It will be considered as limitation of access. Any delay of supply for treatment will be considered limitation of access which will be assessed during the follow-up.

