Cardiovascular devices during follow-up	Treatment	Medical record, Interview	Cardiac resynchronization therapy – defibrillator (CRT-D), Cardiac resynchronization therapy – pacemakers (CRT-P), implantable cardioverter defibrillator (ICD)
Date of prescription of tafamidis	Treatment	Interview	ddmm/yyyy

PFIZER CONFIDENTIAL

CT24-WI-GL02-RF01 6.0 Non-Interventional Study Protocol Template For Primary Data Collection Study 01-

Aug-2023

Page 27 of 57

**CLINICAL AND MEDICAL CONTROLLED DOCUMENT (CMCD)
REQUIRED FORM/TEMPLATE**

Identifier	Version	Title	Effective Date
CT24-WI-GL02-RF01	6.0	NON-INTERVENTIONAL STUDY PROTOCOL TEMPLATE FOR PRIMARY DATA COLLECTION STUDY	01-Aug-2023

Date of first administration of tafamidis	Treatment	Interview	ddmm/yyyy
Delay of supply of tafamidis	Treatment	Interview	Yes, No
Cause of delay	Treatment	Interview	Authorization, Treatment not available in the supplier, error of prescription, other
Adherence	Outcomes	Interview	%
Sum of QRS amplitude in I, II, and III leads at the end of follow-up	Clinical characteristic	Medical record, Interview	mm
Sum of QRS amplitude in all six limb leads at the end of follow-up	Clinical characteristic	Medical record, Interview	mm
Sum of QRS amplitude in all six precordial leads at the end of follow-up	Clinical characteristic	Medical record, Interview	mm
Sokolow-Lyon index low voltage criteria at the end of follow-up	Clinical characteristic	Medical record, Interview	mm
Persistence	Outcomes	Interview	Yes, No
Hospitalization	Outcomes	Interview	Yes, No
Cause of the hospitalization	Outcomes	Interview	Cardiovascular, Other
Date of hospitalization	Outcomes	Interview	Date of admission: dd-mm-yyyy Date of discharge: dd-mm-yyyy
Day(s) of hospitalization	Outcomes	Interview	Days
Quality of life (KCCQ-OS score per visit)	Outcomes	Interview	Score
6MWT [§]	Outcomes	Site	Meters
Scintigraphy (Perugini scale) [§]	Outcomes	Site	Grade 0 - 3

* Per visits, according to schedule of the study

§ According to medical criteria, considering that the physician may choose to perform a different test

PFIZER CONFIDENTIAL

CT24-WI-GL02-RF01 6.0 Non-Interventional Study Protocol Template For Primary Data Collection Study 01-

Aug-2023

Page 28 of 57

**CLINICAL AND MEDICAL CONTROLLED DOCUMENT (CMCD)
REQUIRED FORM/TEMPLATE**

Identifier	Version	Title	Effective Date
CT24-WI-GL02-RF01	6.0	NON-INTERVENTIONAL STUDY PROTOCOL TEMPLATE FOR PRIMARY DATA COLLECTION STUDY	01-Aug-2023

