9.7. Data analysis

9.7.1. Statistical Hypotheses

This is a descriptive, prospective, and observational study. There is no formal hypothesis being tested. The study will describe the clinical and demographic characteristics of ATTR-CM patients. Also, it will describe previous treatments, cardiovascular devices, and comorbidities.

Adherence, persistence, and frequency of hospitalization will be described during the time exposure of treatment.

The change of baseline in the quality of life measured every 3 and 6 months respectively for 24 months.

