3.1 Is the study design described? (e.g., cohort, case-control, cross-sectional, other design)				9.1

¹ Date from which information on the first study is first recorded in the study dataset or, in the case of secondary use of data, the date from which data extraction starts.

² Date from which the analytical dataset is completely available.

**CLINICAL AND MEDICAL CONTROLLED DOCUMENT (CMCD)
REQUIRED FORM/TEMPLATE**

Identifier	Version	Title	Effective Date
CT24-WI-GL02-RF01	6.0	NON-INTERVENTIONAL STUDY PROTOCOL TEMPLATE FOR PRIMARY DATA COLLECTION STUDY	01-Aug-2023

Section 3: Study design	Yes	No	N/ A	Section Number
3.2 Does the protocol specify whether the study is based on primary, secondary, or combined data collection?				9.1
3.3 Does the protocol specify measures of occurrence? (e.g., rate, risk, prevalence)				
3.4 Does the protocol specify measure(s) of association? (e.g., risk, odds ratio, excess risk, rate ratio, hazard ratio, risk/rate difference, number needed to harm (NNH))				9.7.5.2
3.5 Does the protocol describe the approach for the collection and reporting of adverse events/adverse reactions? (e.g., adverse events that will not be collected in case of primary data collection)				10

Comments:

Section 4: Source and study populations	Yes	No	N/ A	Section Number
4.1 Is the source population described?				9
4.2 Is the planned study population defined in terms of:				
4.2.1 Study time period				9.2
4.2.2 Age and sex				9.2
4.2.3 Country of origin				9.2
4.2.4 Disease/indication				9.2
4.2.5 Duration of follow-up				9.2

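### Hospitalisation frequency and hospital days are summarised without a person-time denominator although follow-up can end early, so subgroup summaries mix admission rate with observation time

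*Protocol*

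**What the plan says.** A secondary objective in Section 8 is "To evaluate the frequency of hospitalization and its causes during the follow-up period". Table 2 (Section 9.3) records hospitalisation as yes or no, with its cause, admission and discharge dates, and "Day(s) of hospitalization".

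Section 9.7.5.1 sets the summaries. Binary and categorical items get frequencies and percentages, while "medians and interquartile ranges (IQRs) will be reported for continuous variables, i.e., HRU". HRU is not defined. On subgroups, the Abstract states, and Section 9.7.5.1 repeats, that "difference of means (Student or Welch t-test) or medians (Wilcoxon or Kruskal-Wallis's test) between subgroups will be considered". Section 9.7.3.2 lists the subgroups, among them NYHA class at start of tafamidis and any delay of supply.

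Follow-up length varies by design. Section 9.1 ends it at the earliest of death, withdrawal, or "iii) have terminated of treatment, iv) have been lost to follow up, or, v) finalize the 24 months of following up, the event that happens". Section 9.7.4 uses observed cases without imputation.

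Time enters the hospitalisation analysis in two places. Section 9.7.1 says "Adherence, persistence, and frequency of hospitalization will be described during the time exposure of treatment", and Section 9.1 adds a look-back: "Twelve months before the index date, treatments, and frequency of hospitalization for any causes will be measured". Neither gives a denominator. In Annex 2, item 3.3 asks "Does the protocol specify measures of occurrence? (e.g., rate, risk, prevalence" and so on, and the answer ticked is not applicable.

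**The concern.** How often patients are admitted is a question about events over time. A percentage ever hospitalised, a median number of admissions and a median number of hospital days all grow with the time a patient is watched. Here that time is cut short by death and by stopping treatment, which are plausibly related to how ill the patient is.

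If one subgroup leaves earlier, its summaries fall at the same admission rate, and a truly higher rate is diluted. The direction is not always the same. Delay of supply is assessed during follow-up, so patients watched longer have more chance to be classed as delayed, and they also have more time to be admitted.

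At stake is how a descriptive secondary objective will be read, by subgroup and beside the 12-month look-back.

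**Working it through.** The protocol states no rate, alpha or power, so there is no figure to reproduce. The check asks how far summaries without a denominator move when only observation time differs.

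**Inputs from the protocol.**
- About 50 patients (Section 9.5).
- Maximum follow-up of 24 months from first prescription (Section 9.1).
- Treatment between August 2022 and August 2023 (Section 9.2) and data collection from 15 November 2023 (Section 6). Consent at that start falls about 2.5 to 15.5 months after index.
- Mortality of 29.5% at 30 months on tafamidis, and 3.3 hospitalisations in the first year after diagnosis (Section 7).

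**Assumptions.** Subgroups of 25 v 25; two-sided 5%; exponential exit; gamma-Poisson counts with shape 1 or 2; 0.5, 1.0 or 3.3 admissions per year; early ending by 24 months of 10% v 60%. The exit contrast is illustrative and has no source in the protocol.

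**Percentages.** At 1 admission per year, the chance of at least one is 1 − e^(−1) = 63% over 12 months and 1 − e^(−2) = 86% over 24 months. The yes/no item therefore depends on time observed as much as a count does.

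**Mean follow-up if patients can exit from index.** Hazard h = −ln(1 − p)/2; mean = (1 − e^(−2h))/h.
- p = 0.10: h = 0.0527, mean = 0.10/0.0527 = 1.90 years.
- p = 0.60: h = 0.458, mean = 0.60/0.458 = 1.31 years.

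**Mean follow-up if patients must first reach consent at c years.** Mean = c + (1 − e^(−h(2 − c)))/h. At the midpoint c = 0.75 this gives 0.75 + 1.21 = 1.96 and 0.75 + 0.95 = 1.70 years. Averaged over c from 2.5 to 15.5 months it gives 1.96 v 1.69.

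**Wilcoxon on counts, equal true rates (simulated).**

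| Scenario | Mean follow-up, years | Rejection |
|---|---|---|
| Same exit hazard, −ln(1 − 0.295)/2.5 = 0.140 per year, in both | 1.74 v 1.74 | about 5% |
| 10% v 60%, same hazards, exit only after consent | 1.96 v 1.69 | about 6-10% |
| 10% v 60% early ending among consented patients | 1.94 v 1.57 | about 7-13% |
| 10% v 60%, exit possible from index | 1.90 v 1.31 | 14-35% |

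The upper end of the third row moves by a few points with how the 10% v 60% split is turned into exit hazards after consent.

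**Dilution of a real difference.** Take true rates of 1.0 v 1.5 per year, with the higher rate in the group that exits earlier. Mean count = rate × mean follow-up.
- Exit from index: 1.0 × 1.90 = 1.90 v 1.5 × 1.31 = 1.96, so the difference all but vanishes.
- Exit only after consent: 1.0 × 1.96 = 1.96 v 1.5 × 1.69 = 2.53 (simulated 1.95 v 2.53). The ratio of 1.5 shrinks to about 1.30 but stays visible.

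**Person-time rate ratio.** With exits allowed from index, rejection at equal rates was 4.4-5.6% for Poisson counts and 5.2-6.9% for overdispersed counts, across all follow-up imbalances tried. A true ratio of 1.32 was estimated as 1.30-1.32.

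**The case against.** The strongest reply is that the protocol never says raw admission counts will be tested. HRU is undefined, hospitalisation itself is a yes/no item that takes a percentage, and no per-patient count is defined. This stands: treating hospitalisation as HRU is an inference, though Section 7 does list admissions and hospital days under healthcare resource. It does not remove the problem, because percentages and days depend on observation time too.

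Second, subgroup tests only will be considered, no hypothesis or decision rule exists, and Section 9.9 already concedes that small numbers affect the subgroup analysis. This also stands, and it limits the harm to description.

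Third, denominators and count models are commonly left to the statistical analysis plan, and the wording about exposure time in Section 9.7.1 is compatible with a rate. That is fair as to model choice. But the protocol itself names the summaries and tests, and its checklist sets rates aside as not applicable despite an event-frequency objective.

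A reader might infer that the test rejects simply because follow-up varies between patients. It does not: with the same exit pattern in both subgroups, error stays near 5%. A reader might also infer a built-in doubling of admissions from the 12-month look-back to the 24-month follow-up. The documents plan no such comparison, and the paired tests in Section 9.7.5.2 belong to the exploratory analysis of quality of life and cardiovascular functionality.

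**Conclusion.** The point holds as a reporting defect in a descriptive secondary objective. The stated summaries carry no person-time denominator while follow-up can end early, so patients who leave early contribute too few admissions and days. Where early exit differs between subgroups, differences can be diluted or distorted in either direction.

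The size is modest under the recruitment design: about 6-13% rejection at equal rates under 10% v 60% early ending, against about 5% with equal exit. The 14-35% range needs exits from the index date, which does not fit a cohort that must survive to consent.

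These figures rest on the assumed exit contrast, rates, overdispersion, 25 v 25 split and 5% level. They also assume that admissions before consent are captured and that no patient stops treatment before consent. The rate of 3.3 per year comes from the first year after diagnosis in a four-country database study, not from a treated cohort. The documents do not support calling this a failed test. It is a misleading description that is cheap to avoid.

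**What to change.** In Section 9.7.5.1:
- Define HRU.
- Report admissions and hospital days per patient-year of observed follow-up with 95% CI, alongside the percentage hospitalised.
- Show follow-up time and deaths by subgroup.
- Make any subgroup comparison by a rate ratio from a negative binomial or quasi-Poisson model with log(observed time) as offset.
- Put the 12-month look-back on the same per-patient-year scale.

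In Annex 2, change item 3.3 to Yes.

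The cost is wording and slightly more analysis work. Admission and discharge dates are already in Table 2, and observed time follows from the index date and the end of follow-up.

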9.7.5.2. Bivariate and multivariable analysis

This study does not evaluate any hypothesis. As exploratory analysis and if it is feasible with the number of patients enrolled and distribution of the studied variables, the analysis of the association of baseline characteristics with quality of life and cardiovascular functionality using bivariate and multivariate regression models will be conducted. In terms of distribution of studied continuous variables, a normal test will be conducted in order to determine if it requires a parametric or no parametric test. The test of normality used will be used, frequency distribution (histogram), boxplot, P-P plot (probability-probability plot), and Q-Q plot

PFIZER CONFIDENTIAL

CT24-WI-GL02-RF01 6.0 Non-Interventional Study Protocol Template For Primary Data Collection Study 01-

Aug-2023

Page 33 of 57

CLINICAL AND MEDICAL CONTROLLED DOCUMENT (CMCD) REQUIRED FORM/TEMPLATE

Identifier	Version	Title	Effective Date
CT24-WI-GL02-RF01	6.0	NON-INTERVENTIONAL STUDY PROTOCOL TEMPLATE FOR PRIMARY DATA COLLECTION STUDY	01-Aug-2023

(quantile-quantile plot) to assess normality visually and Kolmogorov-Smirnov (K-S) test and Shapiro-wilk test to evaluate directly (20).

For bivariate analysis, no-parametric tests are necessary due to the variables being of dependent nature by being repeated measures during the follow-up. For continuous variables, paired t-test and Wilcoxon signed ranks test will be used (21).

For multivariable analysis, mixed models will be used, repeated measures analysis of covariance with an unstructured covariance matrix, being patient as random effects and visit and baseline characteristics as fixed effects (22,23).

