9.3.1. Definitions

Kansas City Cardiomyopathy Questionnaire (KCCQ) Score: It is a Patient-reported outcome composed by 23-item, KCCQ that takes 4-6 min to complete. A self-administered questionnaire will be used to measure the patient's perception of their health status within a 2-week recall period. The domains of this scale are: Symptom, Physical function, Social Limitation, self-efficacy, Symptom stability, and Quality of Life. The clinical summary is calculated including the domain Physical limitation and Symptoms. The overall summary score combines total symptoms, physical and social limitation, and Quality of life. The score for each domain has a range from 0-100 where 0 is considered worst health and 100 the best health. Changes in the Overall summary of 5, 10 and 20 points have been considered small but clinically important, moderate to large, and large to very large changes, respectively (12). The scale has been translated and validated to Spanish of Colombia (15).

Perugini grading scale: It is a semi-quantitative method of scoring cardiac uptake following injection of 99mTc-DPD, 99mTc-Pyrophosphate or 99mTc-HMDP scintigraphy (16). It is classified as:

- grade 0: no cardiac uptake and normal rib uptake
- grade 1: cardiac uptake which is less than rib uptake
- grade 2: cardiac uptake with intensity similar rib uptake
- grade 3: cardiac uptake greater than rib uptake with mild or absent rib uptake

6 Minute walk test: It is considered as an alternative to cardiopulmonary exercise test for risk stratification in patients with Heart Failure. It is a simple test that requires no specialized equipment or physicians. It assesses the functional capacity while the patient walks on a flat, solid surface in a period of 6 min (13).

Hospitalization: It is defined as a nonelective admission to an acute care setting for medical therapy that results in at least a 24-hour stay (17).

Cardiovascular causes of hospitalization: The following diseases were considered as cardiovascular causes of hospitalization only it was considered the primary diagnosis (17):

- Heart failure
- Arrhythmia: When the patient is hospitalized by bradyarrhythmia, atrial, or ventricular rhythm disorders of the heart.
- Transient ischemic attack
- Stroke

PFIZER CONFIDENTIAL

CT24-WI-GL02-RF01 6.0 Non-Interventional Study Protocol Template For Primary Data Collection Study 01-

Aug-2023

Page 29 of 57

**CLINICAL AND MEDICAL CONTROLLED DOCUMENT (CMCD)
REQUIRED FORM/TEMPLATE**

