9.5. Study size

Sample size is not required for being observational and descriptive study. The expected number of patients eligible for the study is close to fifty considering the number of patients identified with the diagnosis and the access to the treatment based on the national database of MiPres in Colombia in which each prescription of treatments outside of National Formulary must be registered (19).

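### Section 9.7.5.2 plans bivariate regression for association with baseline characteristics, then assigns the bivariate step to paired tests that carry no information on association

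*Protocol*

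**What the plan says.** The exploratory objective in Protocol section 8 reads: "To analyze the relationship between baseline variables and patient and changes of quality of life and cardiovascular functionality". Section 9.7.5.2 carries it out, on condition that patient numbers and distributions allow, through the "analysis of the association of baseline characteristics with quality of life and cardiovascular functionality using bivariate and multivariate regression models".

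The same section then gives three instructions on how to choose and run the analysis:

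- Normality checks (plots, Kolmogorov-Smirnov, Shapiro-Wilk) are to decide between parametric and non-parametric tests.
- For the bivariate analysis, "no-parametric tests are necessary due to the variables being of dependent nature by being repeated measures during the follow-up". The sentence after it fixes the tests: "For continuous variables, paired t-test and Wilcoxon signed ranks test will be used".
- For the multivariable analysis, a mixed model for repeated measures is to be used, "being patient as random effects and visit and baseline characteristics as fixed effects".

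Elsewhere, section 9.7.5.1 says that Student or Welch t-tests and Wilcoxon or Kruskal-Wallis tests between subgroups will be considered. Section 9.7.3.2 lists those subgroups, and most are baseline characteristics. Sections 8, 9.7.1 and 9.7.2 state that there is no hypothesis and no decision rule.

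**The concern.** The null hypothesis that matches the objective is that change in KCCQ or function does not depend on the baseline variable. The paired t-test and the signed-rank test have another null: that the mean or median within-patient change is zero. A patient's genotype, NYHA class or ejection fraction appears nowhere in either statistic. An analyst who follows the bivariate paragraph therefore obtains p-values for drift over time in a part of the report headed as association.

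The rationale has its own fault. Dependence between repeated measurements calls for a method that respects the pairing or clustering. It does not call for a rank method, which answers doubts about distributional shape. The next sentence names a parametric test, and the preceding paragraph has already made normality the criterion, so the section gives conflicting rules for choosing a test.

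At stake is the reading of the bivariate results. With about fifty patients, and the whole exploratory analysis conditional on feasibility, this simpler step may carry more of the reported evidence than the mixed model does.

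**Working it through.** The protocol gives no sample size calculation, SD, power or significance level, so there is no figure of its own to reproduce. The check asks what the named tests respond to.

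**Inputs from the protocol**

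- n = 50. Section 9.5 says: "The expected number of patients eligible for the study is close to fifty". Section 9.2 says fewer than 50, so n = 30 was also run.
- KCCQ overall summary changes of 5, 10 and 20 points, the sizes that section 9.3.1 grades from small but clinically important up to large or very large.

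**Assumptions, not in the protocol**

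- SD of KCCQ change: 15, 20 or 25.
- Two-sided 0.05 level, for illustration only.
- Normal change scores and a binary baseline factor splitting patients 25/25.

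**Formulas**

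- Paired t-test: t = mean change / (SD/√n), with noncentrality drift × √n / SD.
- Welch test on the change: noncentrality difference / (SD × √(1/25 + 1/25)) = difference / (0.2828 × SD).

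**Case A: drift but no association.** For a 5-point drift the paired noncentrality is 5 × 7.071 / SD = 2.36, 1.77 and 1.41 at SD 15, 20 and 25. With 49 degrees of freedom this gives rejection rates of 63.7%, 41.0% and 28.4%. Simulation (2,000 runs per cell) agrees:

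| n = 50, no association | SD 15 | SD 20 | SD 25 |
|---|---|---|---|
| 5-point drift, paired t | 64% | 40% | 27% |
| 5-point drift, signed-rank | 62% | 39% | 27% |
| 10-point drift, paired t | 99% | 93% | 80% |
| 5- or 10-point drift, Welch by baseline factor | 5–6% | 4% | 4–5% |

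**Case B: association but no overall drift.** One group changes by −10 and the other by +10, a 20-point difference. The overall mean change is zero, so the paired test has nothing to detect. The spread between groups also inflates its standard error, which pushes rejection below 5%. The Welch noncentrality is 20 / (0.2828 × SD) = 4.71, 3.54 and 2.83, giving 99.6%, 93.4% and 79.2%. Simulation:

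| n = 50, 20-point difference | SD 15 | SD 20 | SD 25 |
|---|---|---|---|
| Paired t | 2.2% | 2.8% | 4.0% |
| Signed-rank | 2.0% | 3.0% | 3.9% |
| Welch on the change | 99.7% | 93.4% | 79.5% |

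**Case C: both present.** With a 10-point drift and a 20-point difference, the paired t-test rejects in 98.8%, 89.5% and 74.8%. With the same drift and no association the figures are 99.4%, 93.4% and 80.0%. A real association therefore does not raise the rejection rate; the result is driven by drift.

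The pattern is the same at n = 30. A 10-point drift without association gives paired t rejection of 94%, 74% and 59%. A 20-point difference without drift gives 2–4%, against 94%, 76% and 56% for Welch.

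**Literal pairing.** Pairing a baseline variable directly with KCCQ is no better. For an unrelated age-like variable (assumed mean 75, SD 8, against KCCQ mean 60, SD 20) the paired t-test rejects in 99.7% of runs and a correlation test in about 5%.

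**The case against.** The best defence is that the paired-test sentence was never meant for association. Its reason refers to variables measured repeatedly during follow-up. That describes KCCQ, not baseline characteristics, and section 9.7.1 plans a change from baseline in quality of life, for which paired tests are suitable. The association method would then be the regression in the section's opening sentence. This reading is plausible, but the text does not state it. The paired tests stand under the bivariate heading of the association analysis, with no mention of change over time. If this was the intent, the wording needs correcting.

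A reader might go further and infer that the exploratory objective as a whole would be answered wrongly in both directions, or that no valid test of association is planned. The document does not support that. Bivariate regression is named, the mixed model enters baseline characteristics as fixed effects, and the between-subgroup tests of section 9.7.5.1 are available. These routes have limits. The subgroup tests only will be considered, and they would require continuous predictors such as NT-proBNP to be categorised. The mixed model is the multivariable step.

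It is also fair to say that the analysis is exploratory, conditional and without a decision rule, so the rejection rates show only what the p-value responds to. That a statistic omitting the baseline variable is insensitive to it is true by construction, and the 2–4% depends on changes that cancel exactly across the two halves. These points limit the weight of the finding but do not make the paired tests measure association.

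**Conclusion.** The point holds as an internal contradiction in section 9.7.5.2 together with a mistaken rationale. The section plans regression for association, then assigns the bivariate step for continuous variables to tests whose null is zero within-patient change. The direction of the error needs no assumption, because the baseline variable is absent from the statistics. The size does: the rates above rest on assumed SDs of 15 to 25, an assumed 0.05 level, normal change scores and an even split of the baseline factor.

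The harm is confined to the bivariate step of a conditional exploratory analysis. The primary objective and the other routes to association are not affected. The text should still be changed, because it says the tests will be used and an analysis plan that follows it would inherit the mismatch.

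**What to change.** In section 9.7.5.2:

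1. Delete the sentence saying that dependence makes non-parametric tests necessary.
2. State that the paired t-test and the signed-rank test describe within-patient change from the first measurement only.
3. State that bivariate association uses the single-predictor regression already named, with change in KCCQ (or in function) as outcome and one baseline variable at a time, reporting the slope or between-group difference with a 95% confidence interval.

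The choice of visit, adjustment for the first score and any rank-based alternative can be left to the SAP. The cost is a few sentences of wording and slightly more analysis work. No new data are needed.
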